2.3.3 Selection of Outcomes and Evaluating Efficacy

The goal of a post-CA intervention such as TH will be to not only increase the number of long-term survivors, but to increase the number of survivors with good neurological outcomes. The use of TH following pediatric CA could potentially result in increased numbers of survivors, but also result in more survivors with poor neurological outcomes. Alternatively, TH could be efficacious in children and result in both greater numbers of survivors and more survivors with good neurological outcome. Unfortunately, TH is potentially associated with adverse effects (e.g. arrhythmias, infection risk, neutropenia, bleeding), requiring it to be validated for pediatric efficacy in order to avoid a potentially harmful and somewhat resource intensive intervention in the event it is determined to represent an ineffective therapy.⁴¹ If the efficacy of TH for pediatric CA can be established with an appropriately powered and executed RCT, then major changes in emergency medicine and

critical care therapeutic management of children would be warranted in the US and elsewhere.

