Excessive cooling below the therapeutic range. This complication will be treated by increasing the Blanketrol III temperature so that the patient warms to the therapeutic range (32 to 34°C). Excessive cooling below the therapeutic range in the THAPCA Trials could result in life-threatening cardiac arrhythmias. If cooling below the therapeutic range occurs in patients randomized to receive hypothermia, the patient will be rewarmed to the therapeutic range of 32 to 34°C immediately. Arrhythmias will be managed according to standard AHA PALS guidelines. Excessive cooling will be avoided by utilizing two central temperature probes (esophageal and bladder or rectal) and monitoring subject temperature on a continual basis. The temperature of the water in the Blanketrol III will also be monitored and recorded, and temperature control in all subjects will use the servo-control mechanism available with the Blanketrol III. The patient will not be cooled below 32-34 °C therapeutic range. The study investigator will be contacted for central temperatures of 31.0 °C or less. In the event that the temperature difference between central measures is greater than 1.0 °C, the study investigator will be also be notified.

Cardiac arrhythmias. Serious cardiac arrhythmias are not expected to occur unless the temperature falls well below 30 °C. If a clinically significant arrhythmia develops and persists, then the patient would be rewarmed to normal range if determined by the clinical care team to be necessary.

Infection. Infection rates are expected to be high in both groups of subjects (normothermia and hypothermia groups), based on our prior cohort study data of cardiac arrest patients. The clinical team will utilize antibiotics per their usual clinical site practice in the post arrest population. The THAPCA Trials will monitor both hypothermia and normothermia (control) groups for blood stream and urinary infections as outlined in Section 6.3 of the protocol. In the event of a positive culture or suspicion of possible infection, appropriate antibiotics will be initiated based on the clinical care team's hospital experience.

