Expectedness of the Event: All adverse events, including serious adverse events, will be evaluated as to whether their occurrence was expected or unexpected. An adverse event is considered expected if it is known to be associated with critical illness following cardiac arrest, the underlying medical condition of the subject, is directly related to study outcome (e.g. death), or is otherwise mentioned in the protocol, informed consent, or other study documents. For this protocol, expected events include:

- mortality (unless believed to be related to cooling)
- hemodynamic instability
- cardiac arrhythmias, including life-threatening rhythms
- electrolyte abnormalities
- metabolic acidosis
- sepsis, infections, or bacteremia
- fever
- bleeding
- seizures
- cerebral edema and other brain injury
- worsening neurological function
- renal dysfunction
- liver dysfunction
- reintubation
- hypoxia
- respiratory distress
- pleural effusions
- pulmonary edema
- anasarca (body edema)
- general pediatric problems related to ICU stay and cardiac arrest
- complications related to the condition that led to cardiac arrest

Treatment or Action Taken: For each adverse event, the clinical site will record whether an intervention was required:

- Intervention: Surgery or procedure
- Other Treatment: Medication initiation, change, or discontinuation
- None: No action taken

Finally, the clinical site will record the clinical outcome of each adverse event as follows:

- Death
- Recovered and the patient returned to baseline status
- Recovered with permanent sequelae
- Symptoms continue

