11.2.4 Monitoring Serious Adverse Events

The Principal Investigator of the Data Coordinating Center ([name]) will act as the medical monitor for THAPCA. If [name] is unavailable, a qualified physician will be designated to fulfill this function. Clinical site investigators or coordinators will report a selected subset of expected serious adverse events to the DCC within 24 hours. A detailed completed report will be required to be sent to the DCC within 3 working days of the event,

and the medical monitor will assess these serious adverse events reported from clinical sites in THAPCA. For each of these serious adverse events, the clinical site will provide sufficient medical history and clinical details for a safety assessment to be made with regard to continuation of the THAPCA Trial. The medical monitor will sign each SAE report after review. All SAE reports will be retained at the DCC, and all SAE reports will be available for review by DSMB members and NHLBI staff via the eRoomTM facility.

Serious adverse events that require a written notification of the DCC within 24 hours and a completed written report within three working days of the SAE, and subsequent review by the medical monitor, include the following:

- Mortality
- Infection diagnosed with positive bacterial or fungal culture
- Repeat cardiac arrest
- Life threatening arrhythmias
- Any SAE requiring early cessation of hypothermia
- Any SAE that the clinical site investigator believes should be reported with the supplemental written information.

The other expected serious adverse events that are listed in Section 11.2.1 on page 74 do not require written reporting, but should be recorded in the same manner as all adverse events.

In the unlikely event that the medical monitor believes an unexpected and study-related SAE warrants emergent cessation of enrollment in either or both of the THAPCA Trials, NHLBI staff and the DSMB chairperson will be immediately consulted. If these individuals concur with the judgment of the medical monitor, or if the NHLBI staff and the DSMB chairperson cannot be reached expeditiously, the Data Coordinating Center will notify all clinical site investigators to cease enrollment in the trial. Resumption of enrollment will not occur without consent of the THAPCA Executive Committee, the DSMB, and NHLBI staff.

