11.2.6 Follow-up of Adverse Events

All serious, unexpected and related adverse events, that are unresolved at the time of the patient's termination from the study or discharge from the hospital, will be followed by the investigators until the events are:

- Resolved, subject is lost to follow-up, the adverse event is otherwise explained or has stabilized; OR
- 12 months has passed from the time of randomization

Adverse experiences that begin after discharge from the hospital will not be reported as study adverse events.

12 Data Quality Assurance

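### Serious, non-fatal events rated probably related to cooling still count as expected, and so fall outside the enrolment-cessation, expedited NHLBI and post-discharge follow-up rules

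*Protocol*

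**What the plan says.** Section 11.2.1 gives several ways for an event to be expected: association with critical illness after arrest, association with the underlying condition, a direct link to study outcome, "or is otherwise mentioned in the protocol, informed consent, or other study documents". A list of 21 expected events follows. It includes "cardiac arrhythmias, including life-threatening rhythms", "sepsis, infections, or bacteremia", bleeding and electrolyte abnormalities, none of them qualified by cause. The only qualified item is the first: "mortality (unless believed to be related to cooling".

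Relatedness is rated separately in 11.2.1, against the temperature-control blanket and/or hypothermia. The top category, probably related, is kept for events that other factors cannot reasonably explain.

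Three rules then turn on expectedness:

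- **Cessation of enrolment.** Section 11.2.4 reads "In the unlikely event that the medical monitor believes an unexpected and study-related SAE warrants emergent cessation of enrollment". Section 11.2.5 repeats the restriction, and its route for unanticipated problems also requires an unexpected event.
- **Expedited report to NHLBI.** Section 11.2.5 requires it for serious, unexpected and study-related events and for unanticipated problems.
- **Follow-up after discharge.** Section 11.2.6 covers "All serious, unexpected and related adverse events, that are unresolved at the time of" study termination or hospital discharge. Sections 5.4, 8.4 and 11.2.2 all send the reader there for unresolved events.

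Section 11.2.4 also has a separate route for some expected SAEs: notice to the DCC within 24 hours, a full report within 3 working days, and review by the medical monitor. It covers death, culture-positive infection, repeat arrest, life-threatening arrhythmia, any SAE that forces hypothermia to end early, and any SAE that the investigator chooses to report. Other listed expected SAEs need no written report.

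**The concern.** Expectedness should separate what the underlying illness would produce anyway from what may be new information about the intervention. Here it is fixed by event type, so the relatedness rating cannot change it, except for death. The harms the protocol itself attaches to cooling ("TH is potentially associated with adverse effects (e.g. arrhythmias, infection risk, neutropenia, bleeding" in section 2.3.3) are the ones moved out of reach of the three rules.

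At stake is what happens after a single serious event that the site attributes to cooling or to the blanket. The monitor may be told of it within a day and still have no written rule under which to act. NHLBI gets no active notice. If the child goes home with the event unresolved, the protocol's adverse-event follow-up ends.

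**Working it through.** This is a check of the text; no power or error-rate figure is involved.

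**Step 1: classify each named risk.** Take each event as serious and rated probably related.

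| Event | Expected through | Reaches monitor in 24 h (11.2.4) | Cessation rule | Expedited NHLBI report | Post-discharge follow-up |
|---|---|---|---|---|---|
| Life-threatening arrhythmia, non-fatal | list | yes | no | no | no |
| Culture-positive infection, non-fatal | list | yes | no | no | no |
| Bleeding, non-fatal | list | only if hypothermia ends early or the investigator elects | no | no | no |
| Electrolyte abnormality, non-fatal | list | same condition | no | no | no |
| Neutropenia, non-fatal | mention in 2.3.3 | same condition | no | no | no |
| Skin injury, non-fatal | mention in 7 and 10.4.2 | same condition | no | no | no |
| Death believed related to cooling | excepted, so unexpected | yes | yes | yes | not applicable |

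Of the 21 listed items, 1 has the exception. Of the four hypothermia risks in 2.3.3, three are expected through the list and one (neutropenia) through the mention clause: 4 of 4.

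Both arms are managed on the blanket. The early-cessation trigger refers to hypothermia, so a serious blanket injury in a normothermia child reaches the monitor only if the investigator elects to report it.

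**Step 2: how far the mention clause reaches.** Section 7 mentions significant skin injury only to say that earlier studies reported none. Section 10.4.1 mentions venous thrombosis and intracranial hematoma only as not reported or not increased. Read literally, naming a harm as absent from earlier work makes it expected in this trial.

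**Step 3: read 11.2.4 against itself.** Its first part gives the monitor reports on selected expected SAEs so that a safety assessment bearing on continuation of the trial can be made. Its closing paragraph provides for cessation only for an unexpected, study-related SAE. Apart from cooling-related death, the listed events sent up for that assessment are ones the cessation sentence does not cover.

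**Step 4: a smaller inconsistency in 11.2.1.** The general rule makes death expected as a study outcome, while the list excepts death believed related to cooling. The two should agree.

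**Step 5: scale.** Section 5.6 anticipates 150 to 250 patients a year, and section 11.1 proposes two DSMB meetings a year. Between meetings, 150/2 = 75 to 250/2 = 125 children would be randomised across both trials and both arms. At 1:1, 75/2 = 37.5 to 125/2 = 62.5, or about 38 to 63, would be cooled. This gives the length of the interval in patients; it is not a count of unmonitored children.

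**The case against.** A reader might infer that no cooling-related harm triggers any of the three rules. The protocol does not support that. Death believed related to cooling is excepted, so it is unexpected and reaches both the cessation rule and the NHLBI report.

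A reader might also infer that the affected events go unseen. They do not. Ventricular fibrillation at 33 °C, for instance, is a life-threatening arrhythmia: it goes to the DCC within 24 hours and to the monitor for signed review. Section 11.2.4 makes all SAE reports available to DSMB members and NHLBI staff through eRoom, so what is missing is active expedited notice, not access. The DSMB reviews all adverse events whatever their expectedness and may change its meeting frequency. Infection, arrhythmia, blood-product use and 28-day mortality are compared by arm (9.4). An excess in frequency might be argued to be an unanticipated problem, though that route also requires an unexpected event, and 11.2.1 gives the only definition.

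A third tempting inference is that section 10.4.2 flatly contradicts the list, since it says "Serious cardiac arrhythmias are not expected to occur unless the temperature falls well below 30" °C. That sentence is a forecast about temperature as a cause, while 11.2.1 sets up a reporting category that takes in rhythms due to the arrest itself. Both can stand, but a site could be misled, so the relation should be explained.

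On follow-up, 11.2.6 concerns serious events only, so a non-serious skin injury would drop out in any case. Section 5.4 asks for appropriate follow-up of events that end the study intervention, and families are contacted at three and 12 months. Neither gives continued adverse-event follow-up for every serious related event.

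Finally, classifying by event type is defensible where, as 10.4.2 reports, cohort mortality was nearly 50%. That justifies a list. It does not justify ignoring a rating of probably related once one has been given.

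**Conclusion.** The point holds for serious, non-fatal events of a listed or mentioned type that are rated probably related to cooling or the device. As worded, they fall outside the cessation rule, the expedited NHLBI report and post-discharge follow-up. Two defects carry the finding: section 11.2.4 asks the monitor for a judgement on continuation that its own cessation sentence does not let the monitor act on, and section 11.2.6 drops serious related events of an expected type at discharge. Serious bleeding or skin injury is the least protected, because even the 24-hour route depends on hypothermia ending early or on the investigator's choice.

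This rests on reading the rules literally; a monitor might well act beyond them. Given the 24-hour route, eRoom access and DSMB review of all events, it is a should-fix, not a must-fix.

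**What to change.** 1. In 11.2.4 and 11.2.5, let the medical monitor's cessation rule and the expedited NHLBI report cover any serious event rated probably related to the intervention, whether or not its type is expected.
2. In 11.2.6, follow all serious related events that are unresolved at discharge.
3. In 11.2.1, extend the exception now attached to mortality to the other listed events, in terms that match the protocol's own relatedness definition (blanket and/or hypothermia). Keep the reference to the informed consent, so that disclosed risks remain a benchmark. Narrow the mention clause so that merely naming a harm, for example as not seen in earlier studies, does not make it expected. Align the general statement about death with the listed exception.
4. State how the arrhythmia sentence in 10.4.2 relates to the list in 11.2.1.

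The change is wording in a few subsections. It costs somewhat more expedited reports and a few more children followed after discharge. Design, sample size and analysis are unaffected.

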11.2.2 Time Period for Adverse Events

For purposes of the THAPCA Trials, adverse events occur following randomization through Day 14. Specifically, events that occur following parental permission to participate in THAPCA, but prior to actual randomization, will not be reported as adverse events. These should be recorded as baseline conditions. Events that occur following discharge from the hospital will not be reported as adverse events. Adverse events that occur between randomization and Day 14 that are not resolved by Day 14 will be followed until resolution or hospital discharge, whichever is earlier. If the event has not resolved by hospital discharge, please see section 11.2.6 of the protocol for further instructions.

11.2.3 Data Collection Procedures for Adverse Events

After patient randomization, all adverse events (including serious adverse events), whether anticipated or unanticipated, will be recorded according to the date of first occurrence, severity, and their duration, as well as any treatment prescribed. Any medical condition present at the time of randomization, recorded in the patient's baseline history at study entry, which remains unchanged or improves, will not be recorded as an adverse event at subsequent evaluations. However, worsening of a medical condition that was present at the time of randomization will be considered a new adverse event and reported.

Abnormal laboratory values that are clinically significant will be recorded as adverse events and the clinical site investigator will assess the severity and relationship to the study. Laboratory values that are abnormal at the time of randomization and that do not worsen will not be recorded as adverse events.

Adverse events will be coded using the MedDRA coding vocabulary. Coding will be done centrally at the DCC because this requires specific training.

11.2.4 Monitoring Serious Adverse Events

The Principal Investigator of the Data Coordinating Center ([name]) will act as the medical monitor for THAPCA. If [name] is unavailable, a qualified physician will be designated to fulfill this function. Clinical site investigators or coordinators will report a selected subset of expected serious adverse events to the DCC within 24 hours. A detailed completed report will be required to be sent to the DCC within 3 working days of the event,

and the medical monitor will assess these serious adverse events reported from clinical sites in THAPCA. For each of these serious adverse events, the clinical site will provide sufficient medical history and clinical details for a safety assessment to be made with regard to continuation of the THAPCA Trial. The medical monitor will sign each SAE report after review. All SAE reports will be retained at the DCC, and all SAE reports will be available for review by DSMB members and NHLBI staff via the eRoomTM facility.

Serious adverse events that require a written notification of the DCC within 24 hours and a completed written report within three working days of the SAE, and subsequent review by the medical monitor, include the following:

- Mortality
- Infection diagnosed with positive bacterial or fungal culture
- Repeat cardiac arrest
- Life threatening arrhythmias
- Any SAE requiring early cessation of hypothermia
- Any SAE that the clinical site investigator believes should be reported with the supplemental written information.

The other expected serious adverse events that are listed in Section 11.2.1 on page 74 do not require written reporting, but should be recorded in the same manner as all adverse events.

In the unlikely event that the medical monitor believes an unexpected and study-related SAE warrants emergent cessation of enrollment in either or both of the THAPCA Trials, NHLBI staff and the DSMB chairperson will be immediately consulted. If these individuals concur with the judgment of the medical monitor, or if the NHLBI staff and the DSMB chairperson cannot be reached expeditiously, the Data Coordinating Center will notify all clinical site investigators to cease enrollment in the trial. Resumption of enrollment will not occur without consent of the THAPCA Executive Committee, the DSMB, and NHLBI staff.

11.2.5 Reporting Procedures

Assuring patient safety is an essential component of this protocol. Each participating investigator has primary responsibility for the safety of the individual subjects under his or her care. All adverse events will be evaluated by the clinical site investigator, and will be classified as noted in Section 11.2.1

. All adverse events occurring after study randomization through Day 14 will be recorded and entered into the electronic data entry system provided by the DCC.

The clinical site investigator will report all *serious, unexpected, and study-related* adverse events to the DCC within 24 hours. A detailed completed report will be required to be sent to the DCC within 3 working days of the event. After receipt of the complete report, the DCC will report such *serious, unexpected, and study-related* adverse events to the NHLBI Program Official or Project Officer in an expedited manner (within 24 hours). In accordance with local IRB requirements, the clinical site investigator may be required to report such events to the IRB in addition to notifying the DCC. In the event that the medical monitor believes that such an event warrants emergent suspension of enrollment in either or both of the THAPCA Trials, and NHLBI staff cannot be reached expeditiously, the Data Coordinating Center will notify all clinical site investigators to suspend enrollment in the trial. Resumption of enrollment will not occur without consent of the THAPCA Executive Committee, the DSMB, and NHLBI staff.

Unanticipated problems (UP) are defined as incidents, experiences, or outcomes that are unexpected, related to participation in the THAPCA Trials, and suggest that the research places subjects at a greater risk of harm than was previously known or recognized. The clinical site investigator will report unanticipated problems to the DCC within 24 hours. A detailed completed report will be required to be sent to the DCC within 3 working days of the event. After receipt of the complete report, the DCC will report these unanticipated problems to the NHLBI Program Official or Project Officer in an expedited manner (within 24 hours). In accordance with local IRB requirements, the clinical site investigator may be required to report such unanticipated problems to the IRB in addition to notifying the DCC. In the event that the medical monitor believes that the unanticipated problem warrants emergent suspension of enrollment in either or both of the THAPCA Trials, and NHLBI staff cannot be reached expeditiously, the Data Coordinating Center will notify all clinical site investigators to suspend enrollment in the trial. Resumption of enrollment will not occur without consent of the THAPCA Executive Committee, the DSMB, and NHLBI staff.

After notification of the NHLBI Program Official or Project Officer, and the DSMB chairperson, of *serious, unexpected, and study-related* adverse events or unanticipated problems (UP), decisions will be made whether to continue the study without change, and whether to convene the entire DSMB for an emergent meeting. If a decision is made to suspend enrollment in

either THAPCA trial, this will be reported to all THAPCA investigators, who will be instructed to report this to their local IRB.

The DSMB will review all adverse events (not necessarily serious, unexpected, and study-related) during scheduled DSMB meetings. The DCC will prepare a Summary Report of Adverse Events within 30 days of its meeting, and this report will be distributed to all THAPCA investigators to be forwarded to the local IRB. The Summary Report will contain the following information:

- A statement that a DSMB review of outcome data, adverse events, and information relating to study performance across all centers took place on a given date;
- A statement as to whether or not the frequency of adverse events exceeded what was expected and indicated in the informed consent;
- A statement that a review of recent literature relevant to the research took place;
- The DSMB recommendation with respect to progress or the need for modification of the protocol or informed consent. If the DSMB recommends changes to the protocol or informed consent, the rationale for such changes and any relevant data will be provided;
- A statement that if safety concerns are identified, the NHLBI Program Officer will communicate these promptly to all THAPCA investigators.

